## MODIFIED MEDICATION SATISFACTION QUESTIONNAIRE (MSQ)

Overall, how satisfied are you with your current medication?

Very Dissatisfied	Somewhat Dissatisfied	Neither Dissatisfied nor Satisfied	Somewhat Satisfied	Very Satisfied
				
1	2	3	4	5

Overall, do you prefer your current LAI medication or your previous LAI medication for the treatment of Schizophrenia (prior to your participation in this study)?

Much Prefer Previous LAI	Prefer Previous LAI	Neither Prefer Previous nor Current LAI	Prefer Current LAI	Much Prefer Current LAI
				
1	2	3	4	5

How would you rate the side effects of your current LAI medication, compared with previous LAI medication for the treatment of Schizophrenia (prior to your participation in this current study)?

Much Less Side Effects	Less Side Effects	The Same as Previous	More Side Effects	Much More Side Effects
				
1	2	3	4	5

**APPENDIX K. SIXTH EDITION OF THE TREATMENT SERVICES  
REVIEW (TSR-6) (SAMPLE)**

## TREATMENT SERVICES REVIEW (Version 6) – Modified for Mental Health

This interview asks about different services you may have received over the past \_\_\_ days, since DATE. It includes medical services, emotional or psychological services, family, marital or parenting services, financial or housing services, and legal services. Do you have any questions before we get started?

TIME STARTED: \_\_\_\_\_

### DEMOGRAPHIC INFORMATION

Patient initials:	Interviewer Name:
Patient Number:	Date of Interview:
Patient Marital Status (circle one):	

1. Married

2. Living as married

3. Widowed

4. Divorced

5. Separated

6. Never married

7. No reply

Coverage Period	From: _____ To: _____
NUMBER OF DAYS IN RECALL PERIOD: _____	

G1 Where did you stay for the past ___ days?	# of Days
1. Alone (in private house, apartment, hotel, etc.)	_____-_____-_____-
2. With others (in private house, apartment, hotel, group home, assisted living residence, etc.)	_____-_____-_____-
3. Institution, e.g. hospital, jail, prison (controlled environment) (a) Hospital/Residential treatment	_____-_____-_____-
(b) Jail or prison	_____-_____-_____-
(c) Day treatment or partial hospital program	_____-_____-_____-
4. Homeless shelter	_____-_____-_____-
5. Homeless, i.e. on the street, in an abandoned building, in a car	_____-_____-_____-

## MEDICAL SERVICES

Questions about any medical treatment you have received over the past \_\_\_ days

M1 How many nights were you an inpatient in a medical hospital, nursing home, or medical rehabilitation facility?		
1a) Specify:		
Medical hospital		
Nursing home or medical rehab		
If 0, Skip to M2		
1b) Diagnosis/major problem _____		
1c) Major procedures or evaluations _____		
? ON PAST ___ DAYS WHEN NOT IN A MEDICAL HOSPITAL:		
M2 How many times did you visit an emergency room ?		
IF 0, SKIP TO M3		
2a) What was your reason(s) for visiting the ER? Check all that apply:		
Medical		
1 – Yes		
2 – No		
Psychological		
1 – Yes		
2 – No		
Substance Use		
1 – Yes		
2 – No		
2b) Diagnosis/major problem _____		
2c) Major procedures or evaluations _____		
M3 How many times did you visit a medical doctor (physician, psychiatrist) for testing, examination, treatment, or care of medical concerns/problems?		
Note: we will ask you about visits for psychological or emotional concerns later.		
If 0, SKIP TO M4		
3a) Diagnosis/major problem _____		
3b) Major procedures or evaluations _____		
M4 How many times did you visit any other medical professional (e.g. dentist, optometrist, nurse, physical therapist, X-ray or lab technician) for testing, examination, or treatment of medical concerns/problems?		
If 0, SKIP TO M5		
4a) Diagnosis/major problem _____		
4b) Major procedures or evaluations _____		

M5	How many (individual or group) counseling sessions did you attend with non-medical personnel during which medical concerns/problems were the main focus (exclude all previously recorded visits)?		
If 0, SKIP TO M6			
5a) Number of sessions with:			
Non-medical doctor (e.g. psychologist – Ph.D./Psy. D) _____			
Physician assistant, Nurse prescriber (Practitioner, APNP) _____			
Nurse _____			
Other clinician (e.g. counselor, social worker, case manager, clergy) _____			
Group member(s) (i.e. a support group not professionally led) _____			
Don't know _____			
5b) On average, how long did a session last? (record # of minutes) _____ mins			
5c) How many of these were group sessions? _____			
PSYCHOLOGICAL SERVICES			
Questions about any emotional or psychological services received over the past _____ days			
P1	How many nights were you an inpatient in a psychiatric hospital or psych treatment unit (i.e., stayed overnight)? Where? _____		
1a) Diagnosis/major problem _____			
1b) Major procedures or evaluations _____			
? On past _____ days NOT in psychiatric inpatient treatment:			
P2	On how many days did you attend any treatment for mental health, emotional or psychological problems?		
Where? _____			
2a) How many of these were day hospital or intensive outpatient programs? _____			
P3	How many individual (one-on-one) sessions did you attend during which your mental health, emotional or psychological problems were the main purpose of the discussion (not including inpatient or day hospital/intensive outpatient programs)?		
If 0, SKIP TO P4			
3a) Number of individual sessions with:			
Medical doctor (e.g. psychiatrist or physician) _____			
Non-medical doctor (e.g. psychologist – Ph.D./Psy. D.) _____			
Physician assistant, Nurse prescriber (Practitioner, APNP) _____			
Nurse _____			
Other clinician (e.g. counselor, social worker, case manager, clergy) _____			
Group member(s) (i.e. a support group not professionally led) _____			
Don't know _____			
3b) On average, how long did each individual session last? (# of minutes) _____ mins			

P4	How many group sessions did you attend for mental health, emotional or psychological problems?		
If 0, SKIP TO FAMILY SERVICES			
4a) Number of group sessions with:			
Medical doctor (e.g. psychiatrist or physician) _____			
Non-medical doctor (e.g. psychologist – Ph.D./Psy. D.) _____			
Physician assistant, Nurse prescriber (Practitioner, APNP) _____			
Nurse _____			
Other clinician (e.g. counselor, social worker, case manager, clergy) _____			
Group member(s) (i.e. a support group not professionally led) _____			
Don't know _____			
4b) On average, how long did a group session last? (# of minutes) _____ mins			
4c) On average, how many other patients were in a group? _____			
4d) On average, how many group leaders were present in each session? _____			

#### ***FAMILY SERVICES***

Questions about family or parenting services received over past \_\_\_\_ days.

F1	How many classes or sessions did you attend to help with parenting or problems with children?		
If 0, SKIP TO F3			
1a) Number of sessions with:			
Medical doctor (e.g. psychiatrist or physician) _____			
Non-medical doctor (e.g. psychologist – Ph.D./Psy. D.) _____			
Physician assistant, Nurse prescriber (Practitioner, APNP) _____			
Nurse _____			
Other clinician (e.g. counselor, social worker, case manager, clergy) _____			
Group member(s) (i.e. a support group not professionally led) _____			
Don't know _____			
1b) On average, how long did a session last? _____ mins			
1c) In how many of these sessions were members of other families present? _____			
F2	How many treatment sessions did you attend with some member(s) of your family or significant other? (exclude those recorded in previous sections)		
2a) Number of those with:			
Medical doctor (e.g. psychiatrist or physician) _____			
Non-medical doctor (e.g. psychologist – Ph.D./Psy. D.) _____			
Physician assistant, Nurse prescriber (Practitioner, APNP) _____			
Nurse _____			
Other clinician (e.g. counselor, social worker, case manager, clergy) _____			
Group member(s) (i.e. a support group not professionally led) _____			
Don't know _____			

2b) On average, how long did a session last? (# of minutes)		____ mins
2c) In how many of these sessions were members of other families present?		____
F3 How many sessions did you attend to deal with relationship issues (e.g. domestic violence, communication issues) where no other family member was present? (exclude any previously recorded)		____
3a) Number of those with:		
Medical doctor (e.g. psychiatrist or physician)		____
Non-medical doctor (e.g. psychologist – Ph.D./Psy. D.)		____
Physician assistant, Nurse prescriber (Practitioner, APNP)		____
Nurse		____
Other clinician (e.g. counselor, social worker, case manager, clergy)		____
Group member(s) (i.e. a support group not professionally led)		____
Don't know		____
3b) On average, how long did a session last? (# of minutes)		____ mins
3c) How many of these were group sessions?		____

#### *FINANCIAL/EMPLOYMENT/HOUSING SERVICES*

Questions about any specialized educational, financial, employment, or housing services received over the past \_\_\_\_ days.

E1 How many days did you attend school or formal training (e.g. apprenticeship, internship)?		____
E2 How many days did you work in a therapeutic work setting/sheltered workshop ?		____
E3 How many sessions did you attend where job/education counseling or placement was the main focus?		____
3a) Number of those with:		
Job or education counselor		____
Anyone else (i.e. non-specialist)		____
E4 How many sessions did you attend where specific housing services were the main focus?		____
4a) Number of those with:		
Any housing specialist		____
Anyone else (i.e., non-specialist)		____

E5	How many sessions or classes did you attend where financial/benefits issues were main focus?		_____
5a)	Number of those with:		
	Benefits or financial counselor, or any other financial specialist?		_____
	Anyone else (i.e. non-specialist)		_____

### **LEGAL SERVICES**

Following questions concern any legal or correctional involvement over past \_\_\_\_ days.

L1	Have you been arrested, picked up, or transported by police in the last ____ days? YES OR NO		1 – Yes 2 – No
1a)	If yes, why? (Check all that apply)		
	Vagrancy (street person/begging/homelessness/transient)		1 – Yes 2 – No
	Related to Drug/Alcohol use or possession		1 – Yes 2 – No
	Disorderly conduct/disturbing the peace		1 – Yes 2 – No
	Public endangerment		1 – Yes 2 – No
	Other: _____		1 – Yes 2 – No
1b)	If yes, for how many days were you incarcerated?		_____

### **OTHER SERVICES**

O1	Did you receive any other services during past ____ days (e.g. food bank, soup kitchen)?		1 – Yes 2 – No
1a)	Specify: _____		
1b)	Specify: _____		
1c)	Specify: _____		
1d)	Specify: _____		
O2	In the past ____ days, did someone help you manage your overall condition – including your physical health, mental health, social, housing, financial and legal situation – by giving you information about the kind of help that is available or by putting you in touch with others who could help you? (e.g. case management) [not including services already recorded]		1 – Yes 2 – No
2a)	On how many days did you meet/speak with him/her?		_____

**03** Throughout this interview, you've told me about different services you've received over the past \_\_\_ days [give examples of services patient has described]. I realize things aren't that cut and dried – I know, for example, that you don't just talk about medical issues; you can talk about social or emotional or family or medical problems. The same is true when you go to the doctor – you don't just talk about medical problems; you can talk about emotional issues or a lot of other things. What I'd like to do now is to get a sense of that. Given all the services and treatments and contacts you've had in the past \_\_\_ days, how much of all of that dealt with:

3a) Your physical health or medical problems?

0	1	2	3	4
None	A little bit	Some	Quite a bit	A lot

3b) Your mental health or psychological problems and issues?

0	1	2	3	4
None	A little bit	Some	Quite a bit	A lot

3c) Your family problems and issues?

0	1	2	3	4
None	A little bit	Some	Quite a bit	A lot

3d) Your employment, education, finances, or house?

0	1	2	3	4
None	A little bit	Some	Quite a bit	A lot

3e) Your legal or criminal problems and issues?

0	1	2	3	4
None	A little bit	Some	Quite a bit	A lot

**TIME ENDED:** \_\_\_\_\_

**APPENDIX L. CAREGIVER QUALITY OF LIFE (CARERQOL) –  
BURDEN DIMENSIONS (7D) [BROUWER WBF, 2006]  
AND VISUAL ANALOG SCALE (VAS) (SAMPLE)**

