### **5.2. Secondary Objectives**

The secondary objectives of this study are to:

- Evaluate quality of life, including daily and social functioning, after treatment with aripiprazole lauroxil
- Characterize the caregiver and healthcare burden

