## 7.3.15. Other Assessments

### 7.3.15.1. Sixth edition of the Treatment Services Review (TSR-6)-Modified for Mental Health

The modified TSR-6 ([Appendix K](#)) is a brief structured interview to assess specific services provided to patients; this version was modified for use in a patient population for chronic mental illness. The modified TSR-6 focuses on services for five potential problem areas: medical condition, employment and support, legal status, family/social relations, and psychiatric function. Patients are asked about the services that they received in the past 28-42 days. The modified TSR-6 consists of 22 items; it will be administered at the time points identified in [Table 1](#).

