## **14. STATISTICS**

### **14.1. Sample Size Considerations**

No formal sample size calculations have been performed. The sample size is based on clinical considerations.

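### In the TSR-6 form (Protocol Appendix K), a zero answer at F1 skips F2, so treatment sessions attended with family go unasked and can only be under-recorded

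*Protocol*

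**What the plan says.** Protocol section 7.3.15.1 describes the instrument as a structured interview on services received. It covers five problem areas, one of them family and social relations. The section also gives the length: "The modified TSR-6 consists of 22 items". Protocol Table 1 schedules the interview at Screening, Day 1 and Months 1 to 6. Protocol sections 7.1 and 12 name it as the measure of total healthcare costs, which bears on the secondary objective in section 5.2: "Characterize the caregiver and healthcare burden". SAP sections 1.2 and 3.7.14 provide for a listing and nothing more.

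The form is in Protocol Appendix K, which is labelled a sample. Its Family Services block has three questions:

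- **F1** begins "How many classes or sessions did you attend to help with" and concerns being a parent or difficulties with children. The instruction beneath it sends a zero answer to F3.
- **F2** begins "How many treatment sessions did you attend with" and concerns sessions attended jointly with a relative or partner. It carries the note "exclude those recorded in previous sections". Sub-items 2a to 2c record the type of provider, the average length, and how many sessions included other families.
- **F3** counts sessions on relationship issues at which "no other family member" was present.

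The interview closes with O3. The subject rates from 0 to 4 how much of all contact in the period dealt with each of five topics. The family topic is "3c) Your family problems and issues".

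**The concern.** F1 acts as a gate for F2, but the two questions are about different things. A subject without children, or with no need of parenting help, can still attend treatment sessions with a relative or partner. Following the form as printed, the interviewer never asks that subject about them.

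At stake is the completeness of one of the five service areas in the instrument that the protocol names for healthcare costs. The error runs one way: joint sessions can be missed but not added. Joint sessions are plausible in this trial, because inclusion criterion 10 requires every subject to have an identified caregiver. The missing sub-items matter too, since provider type and session length are what anyone costing a session would need.

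**Working it through.** No power or precision calculation is involved. Protocol section 14.1 says "No formal sample size calculations have been performed". The check is a count of items and a trace of the printed skips.

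**1. Reproduce the stated length.** Numbered questions in Appendix K: G1 (1) + M1–M5 (5) + P1–P4 (4) + F1–F3 (3) + E1–E5 (5) + L1 (1) + O1–O3 (3) = 22. This matches section 7.3.15.1, and it does so only with F2 counted. F2 is therefore part of the instrument as the protocol describes it.

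**2. Trace every skip.** Eight are printed:

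| Question answered zero | Skip target | Printed item passed over |
|---|---|---|
| M1 | M2 | none |
| M2 | M3 | none |
| M3 | M4 | none |
| M4 | M5 | none |
| M5 | M6 (not on the form) | none; next printed item is P1 |
| P3 | P4 | none |
| P4 | Family Services | none |
| F1 | F3 | F2, with 2a–2c |

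Six of the eight lead to the next item or section. One points to a question that does not exist. Only the F1 skip passes over a printed question. With F1 = 0 a subject can reach at most 22 − 1 = 21 items; with F1 above zero, all 22.

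**3. Can F3 recover the sessions?** No. F3 is confined to sessions without family present and F2 to sessions with a relative or partner, so the two do not overlap.

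**4. Can earlier sections recover them?** In part. F2's own note shows that the form expects some joint sessions to have been entered already. P2 counts days of any mental health treatment and P4 counts group sessions; neither rules out family being there. P3 is limited to one-on-one sessions, however, and a session with a single relative is not obviously a group session. P2 does not collect provider type or session length. What is lost is the set of joint sessions not entered earlier, together with the F2 detail on them.

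**5. How often can it recur?** Table 1 marks the TSR-6 at Screening, Day 1 and six monthly visits: 1 + 1 + 6 = 8 interviews. A subject dosed every 6 weeks may skip Months 1 and 4: 8 − 2 = 6. F2 is omitted at each of these interviews where F1 = 0.

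**6. Does item 3c depend on F2?** No. The O3 stem has the interviewer mention services already described, but the rating covers everything the subject received in the period. The form has no scoring rule that links 3c to F1–F3.

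**The case against.** The strongest case on the other side is that little depends on this. The SAP plans no summary of F2, no summary of 3c and no cost calculation, so no planned estimate is biased. F2 is one of 22 items. The protocol places the TSR-6 among assessments collected for exploration. Appendix K is a sample, and neither the fielded form nor the eCRF routing is in the documents, so the raters may have worked from a corrected form. All of this stands and keeps the severity low. It does not remove the fault, because the listing is the only planned output and an incomplete entry carries straight into it.

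A reader might infer three stronger things that the documents do not support.

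- *That item 3c is unreliable.* It is a direct self-rating of all contact in the period. A subject never asked F2 can still answer it correctly. At most the interviewer has fewer examples to offer as prompts.
- *That family treatment is recorded only for subjects who attend parenting sessions.* F2's exclusion note, with P2 and P4, shows that some joint sessions can be entered elsewhere.
- *That a blank F2 cannot be told from a true zero.* The skip is deterministic. F1 = 0 with F2 blank means not asked, whereas a true zero is an entered 0. The risk is only that someone using the listing overlooks this.

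**Conclusion.** The routing error is real and minor. At every interview with F1 = 0, the form as printed omits F2 and its sub-items, and joint sessions not entered in earlier sections go unrecorded. The effect is confined to the family-services part of the TSR-6 listing and to any healthcare cost later derived from it. Through this route, both can only be understated.

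The size cannot be computed. It might be tempting to assume a share of subjects with no parenting classes and multiply by the roughly 50 planned. The documents give no such share, and the product would count subjects not asked rather than sessions lost. A loss needs three things together: F1 = 0, a session with family, and no earlier entry. The documents inform none of these.

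The conclusion assumes that the fielded form matches the sample and that interviewers followed the printed skips. M5's pointer to a missing M6 suggests that the skip targets were not fully checked. Why is unknown, since the unmodified instrument is not in the documents.

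**What to change.** 1. Check the fielded form and the eCRF routing against Appendix K before changing anything.
2. Redirect F1's zero-answer skip from F3 to F2.
3. Make F2 a required entry in the eCRF at every interview, whatever the answer to F1.
4. For interviews already held with F1 = 0 and F2 blank, show F2 in the listing as not asked, never as 0, and apply the same rule in any cost calculation.
5. Point M5's zero-answer skip to P1. This is clerical; no data are lost through it.

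The cost is two edits to the form, one edit check, a note in the listing specification, and one more question at interviews with F1 = 0, plus its sub-items when the answer is above zero.

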## CarerQol-7D

Please draw an "X" to indicate which description best fits your current care giving situation

no      some      a lot of

a. I have    fulfillment with carrying out my care tasks.

b. I have    relational problems with the care receiver (e.g., he/she is very demanding, he/she behaves differently, we have communication problems).

c. I have    problems with my own mental health (e.g., stress, fear, gloominess, depression, concern about the future).

d. I have    problems combining my care tasks with my daily activities (e.g., household activities, work, study, family and leisure activities).

[figure not shown]
e. I have    financial problems because of my care tasks.

f. I have    support with carrying out my care tasks, when I need it (e.g., from family, friends, neighbors, acquaintances).

g. I have    problems with my own physical health (e.g., more often sick, tiredness, physical stress).

## CarerQol-VAS

Please draw an "X" on the scale below to indicate how happy you feel at this moment

Derived from Brouwer WB, van Exel NJ, van Gorp B, Redekop WK. The CarerQol instrument: a new instrument to measure care-related quality of life of informal caregivers for use in economic evaluations. Qual Life Res. 2006 Aug;15(6):1005-21.

**APPENDIX M. BURDEN ASSESSMENT SCALE (SAMPLE)**

### Burden Assessment Scale (BAS)

I am going to read a list of things which other people have found to happen to them because of their relative's illness. Would you tell me to what extent you have had any of the following experiences in the past six months.

Not at all 1	A little 2	Some 3	A lot 4	N/A 9
-----------------	---------------	-----------	------------	----------

Because of (name's) illness, to what extent have you:

1. Had financial problems
2. Missed days at work (or school)
3. Found it difficult to concentrate on your own activities
4. Had to change your personal plans like taking a new job, or going on vacation
5. Cut down on leisure time
6. Found the household routine was upset
7. Had less time to spend with friends
8. Neglected other family members' needs
9. Experienced family frictions and arguments
10. Experienced frictions with neighbors, friends, or relatives outside the home
11. Became embarrassed because of (name's) behavior
12. Felt guilty because you were not doing enough to help
13. Felt guilty because you felt responsible for causing (name's) problem
14. Resented (name) because s/he made too many demands on you
15. Felt trapped by your caregiving role
16. Were upset about how much (name) had changed from his or her former self
17. Worried about how your behavior with (name) might make the illness worse
18. Worried about what the future holds for (name)
19. Found the stigma of the illness upsetting

Burden Assessment Scale, Reinhard SC, Gubman GD, Horwitz AV, Minsky S. Burden Assessment Scale for families of the seriously mentally ill. Evaluation and Program Planning. 1994;17(3):261-269.

